### 5.1.3 Exploratory Endpoints

- **Clinical benefit rate (CBR)** is the proportion of subjects who have the best overall response (confirmed) of CR or PR or durable SD. A stable disease (SD) must be at  $\geq 5$  weeks after the first study dose. A durable SD is a subset of SD with the duration of  $\geq 23$  weeks after the first study dose.
- **Disease control rate (DCR)** is the proportion of subjects who have the best overall response (confirmed) of CR, PR or SD.
- **Duration of response (DOR)** is defined as the time from the first objective response (i.e., the initial CR or PR that was confirmed) to the first documented disease progression or death. This endpoint is just defined for the subjects who had confirmed response during study.
- Evaluate the association of tumor and blood biomarkers with clinical outcomes, including efficacy.

## 5.2 Study Subjects

### 5.2.1 Definitions of Analysis Sets

The Full Analysis Set [FAS] will include all subjects who received at least one dose of lenvatinib. The FAS will be the population for the safety analysis. Some selected efficacy endpoints will also be summarized in the FAS.

The Evaluable Analysis Set [EAS] will include FAS subjects with histological diagnosis of ATC that was confirmed by central pathology review. The EAS will be the primary population for the efficacy analysis.

### 5.2.2 Subject Disposition

The number (percentage) of enrolled (i.e., signed informed consent) and treated subjects will be summarized as well as reasons for discontinuation from study treatment. Survival status at the last follow-up visit, and reasons for screen failure, will also be summarized.

### 5.2.3 Protocol Deviations

Major protocol deviation criteria will be established and subjects with major protocol deviations will be identified and documented before the database lock for the primary analysis.

Major protocol deviations will be summarized and listed by each category. All protocol deviations identified according to the study entry criteria and during treatment will be listed.

### 5.2.4 Demographic and Other Baseline Characteristics

Demographic and other baseline characteristics for both the FAS and EAS will be summarized for lenvatinib treatment, using descriptive statistics. Continuous demographic and baseline variables include age, BMI, weight, and height; categorical variables include sex, age group (<65 years, 65-75, >75 years), region, ethnicity and race. Other variables at study entry include: pregnancy test, ECOG performance status, time since disease progression, prior radiotherapy (yes/no), ATC diagnosis confirmation by central pathology review (yes/no), TNM classification (T-Primary Tumor, N-Regional Lymph Nodes, M-Distant Metastasis), Anaplastic Thyroid Cancer Stage (IVA, IVB, IVC), time from original histological diagnosis to first dose, NYHA, number of target lesions and sum of target lesion diameters.

### **MEDICAL HISTORY**

The number (percentage) of subjects in the FAS reporting a history of any medical condition and current medical condition, as recorded on the CRF, will be summarized. A subject data listing will be provided. Medical History will be coded using MedDRA (version 21.0 or newer), and summarized on the FAS by System Organ Class and Preferred term.

### 5.2.5 Prior and Concomitant Therapy

All investigator terms (verbatim terms) for medications recorded in the CRF will be coded to an 11-digit code using the World Health Organization Drug Dictionary (WHO DD) (WHODDMAR2018). The number (percentage) of subjects who took prior and concomitant medications will be summarized in FAS by Anatomical Therapeutic Chemical (ATC) class, and WHO DD preferred term.

Prior medications are defined as medications that stopped before the first dose of study drug. Concomitant medications are defined as medications that (1) started before the first dose of study drug and were continuing at the time of the first dose of study drug, or (2) started on or after the date of the first dose of study drug up to 28 days after the subject's last dose. All medications will be presented in subject data listings.

Frequencies [n (%)] of previous anti-cancer procedures will be summarized similarly by system organ class and preferred term. In addition, previous anti-cancer medications will be summarized in terms of number of prior regimens, duration of last therapy, best response for last therapy, time from end of last therapy to first dose, and indication of previous medication

(neoadjuvant/adjuvant/metastatic/unknown). The following data on radiotherapy will be summarized: time from last radiotherapy to first dose, site of previous radiotherapy, progression of tumor lesion at the site since radiotherapy (yes/no), and number of all prior radiotherapy treatments.

### 5.2.6 Treatment Compliance

Records of treatment compliance for each subject will be kept during the study. Clinical research associates will review treatment compliance during investigational site visits and at the completion of the study. Treatment compliance will not be summarized since the data will not be entered in the clinical database.

## 5.3 Data Analysis General Considerations

All efficacy analyses will be summarized with available data in the clinical database at the data cutoff.

### 5.3.1 Pooling of Centers

Subjects from all centers will be pooled for all analyses.

### 5.3.2 Adjustments for Covariates

No adjustments for covariates will be performed in the study.

### 5.3.3 Multiple Comparisons/Multiplicity

Per protocol, the type I error calculation for the primary efficacy analysis did not factor in the descriptive interim analysis, the interim decision won't affect the overall type I error in the formal primary analysis; no multiplicity adjustments for the tests of secondary endpoints will be made in this study.

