9.7.1.6.2 SECONDARY EFFICACY ANALYSES

PFS is defined as the time from the date of beginning of lenvatinib administration to the date of first documentation of disease progression or death, whichever occurs first.

PFS censoring rule will follow FDA Guidance for Industry, Clinical Trial Endpoints for Approval of Cancer Drugs and Biologics (2007).

Subjects who have a clinical determination of progression should undergo an MRI, if possible, to correlate radiographic findings with the clinical findings. If a clinical determination of progression for a subject is confirmed by an MRI scan, the date of the MRI scan will be considered as the progression date for that subject. Data for subjects without disease progression or death at the time of analysis will be censored at the time of the last tumor assessment. Data for subjects who are lost to follow-up prior to documented disease progression will be censored at the last tumor assessment date when the subject is known to

be progression-free. Data for subjects who start to receive new anticancer therapy will be censored at the last tumor assessment date prior to the introduction of new therapy. More details will be given in the SAP.

A 12-week PFS of $\geq 70\%$ in single agent lenvatinib and 50% in the historical control (corresponding to a median PFS improvement of approximately 3 months assuming exponential distribution) are assumed in the hypothesis testing:

$$H_0: 12\text{-week PFS} = 50\%$$

$$H_a: 12\text{-week PFS} \geq 70\%$$

Kaplan-Meier (KM) method will be used to estimate 12-week PFS, along with the corresponding 95% CI constructed using Greenwood's formula ([Greenwood, 1926](#); [Collett, 1994](#)). The CI approach will be used to demonstrate the superiority of 12-week PFS in the single agent lenvatinib over historical control. If the lower bound is above 50%, it will be concluded that the single agent lenvatinib statistically significantly increases 12-week PFS compared with historical control.

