Overall survival is defined as the time from the date of beginning of lenvatinib administration until date of death from any cause. Six-month OS is assumed to be approximately 44% in the historical control (corresponding to a median OS of approximately 5 months assuming an exponential distribution). Six-month OS and its 95% CI will be calculated using the same methods as described in the 12-week PFS analyses. If the lower bound of 95% CI for 6-month OS is above 44%, it will be concluded that the single agent lenvatinib statistically significantly increases 6-month OS compared with historical control.

Median PFS and median OS will be estimated using the KM method. Their 2-sided 95% CIs will be constructed with a generalized Brookmeyer and Crowley method ([1982](#)). KM estimates of PFS and OS will be plotted over time.

Secondary efficacy endpoints will be analyzed sequentially, as listed above.

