9.7.1.6.4 FORMAL ANALYSES

A formal analysis will be carried out approximately 6 months following the enrollment of the last subject. The timing of the formal analysis is chosen such that the secondary endpoints, 12-week PFS and 6-month OS, will be adequately described. The primary population for efficacy analysis is EAS. Efficacy and safety analysis will also be performed in FAS.

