9.7.5 Procedure for Revising the Statistical Analysis Plan

The SAP will be finalized prior to the database lock in this trial. Any deviation from analysis plan described in the protocol will be documented in the SAP.

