## 4 DETERMINATION OF SAMPLE SIZE

The sample size calculation was based on the assumed objective response rate (ORR), defined in Section 5.1) of 27% in the trial as compared to 10% in the historical control. Using a binomial exact test, the power was 0.932 with 57 evaluable subjects to demonstrate statistical significance at a 1-sided alpha of 0.025. To evaluate the power in the secondary endpoint 12-week PFS (defined in Section 5.1), an exponential distribution assuming 12-week PFS being 70% was used to simulate PFS data. Censoring times were generated such that the average number of observed PFS events was approximately 45 in the 57 evaluable subjects. In the 5,000 simulation runs, the lower bound of 95% confidence interval for PFS at 12 weeks was greater than 50% (historical control), 87.7% of the time. Hence, the power was 0.877 in demonstrating statistical superiority of the 12-week PFS in single agent lenvatinib. Similarly, approximately 35 observed OS events in 57 evaluable subjects yielded a power of approximately 0.857 in demonstrating a statistically significant increase in 6-month OS over historical control. Assuming ATC confirmation rate was 75% in the enrolled subjects, approximately 76 subjects would need to be enrolled. Subjects deemed to have another diagnosis (not ATC) would be replaced for the purpose of efficacy analyses.

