### 5.4.2 Secondary Efficacy Analyses

All analyses of secondary efficacy endpoints will be performed in FAS.

Progression-Free Survival (PFS) and Overall Survival (OS) will be analyzed using Kaplan-Meier product-limit method. The Kaplan-Meier estimated rate of event-free will be presented at 12 weeks for PFS and at 6 months for OS, together with the corresponding two-sided 95% CI. In addition, the median, first and third quartiles of the Kaplan-Meier estimated event-free time will also be presented together with the corresponding 95% Brookmeyer-Crowley (or generalized Brookmeyer-Crowley) CI.

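### The SAP keeps secondary tests without adjustment but omits the claim thresholds and testing order, and moves these analyses from EAS to FAS without recording it

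*SAP*

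**What the plan says.** **Protocol.** Section 9.7.1.6.2 sets hypotheses for 12-week PFS (50% against 70% or more) and states: "The CI approach will be used to demonstrate the superiority of 12-week PFS". The condition is a lower 95% bound above 50%. For 6-month OS the rule is: "If the lower bound of 95% CI for 6-month OS is above 44%, it will be concluded" that OS is significantly increased. The section then adds median PFS and median OS, which have no null value, and closes with: "Secondary efficacy endpoints will be analyzed sequentially, as listed above". It does not say what happens to later endpoints if an earlier one fails, or whether ORR must succeed first. On the analysis set, section 9.7.1.6.4 says: "The primary population for efficacy analysis is EAS", and adds that efficacy will also be analyzed in the FAS. Section 9.7.5 says: "Any deviation from analysis plan described in the protocol will be documented in the SAP".

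**SAP.** Section 4 keeps the power statements for both endpoints, including the one for "demonstrating a statistically significant increase in 6-month OS over historical control". Section 5.3.3 says that "no multiplicity adjustments for the tests of secondary endpoints will be made in this study". Section 5.2.1 repeats that the EAS is primary for efficacy, but section 5.4.2 says: "All analyses of secondary efficacy endpoints will be performed in FAS". Section 5.4.2 then describes only the presentation of Kaplan-Meier rates, medians and quartiles with confidence intervals. The 50% benchmark appears only in the section 4 power text, and 44% appears nowhere in the SAP. Section 7 lists two changes: exposure in months instead of cycles, and no biomarker analyses.

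**The concern.** The SAP speaks of tests and keeps the power for them, but it contains no decision rule for them. For ORR, by contrast, section 5.4.1 restates the hypotheses and the p-value criterion in full. Two workable readings remain. In one, each endpoint is claimed on its own 95% interval. In the other, 6-month OS may be claimed only after 12-week PFS has succeeded. A sentence that rules out multiplicity adjustment fits both, because a fixed sequence needs no adjusted alpha.

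The readings differ in one situation: PFS misses its threshold and OS passes. In a single-arm trial against assumed historical rates, a statement that OS is significantly increased carries weight, so whether it may be made should be settled before database lock. The analysis set matters for the same reason. The powers were computed for 57 evaluable subjects, and a threshold rule cannot be applied until the set is named.

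**Working it through.** **1. Inputs.** ORR 10% against 27%, one-sided 0.025, n = 57, power 0.932. 12-week PFS 50% against 70%, about 45 events in 57, power 0.877. 6-month OS null 44%, about 35 events in 57, power about 0.857, alternative not stated. All come from protocol 9.7.1.6 and 9.7.2 and SAP section 4. The correlations below are assumptions.

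**2. The plan's own figures.** For ORR, rejecting at 11 or more responders of 57 gives error 0.0242 and power 0.9321, matching 0.932. For PFS, 5,000 simulated trials (exponential times, 70% at 12 weeks, censoring set to about 45 events, plain Greenwood interval) give power 0.875 with uniform and 0.876 with exponential censoring, close to 0.877. OS power cannot be reproduced strictly without an alternative. An assumed 65% with uniform censoring gives 0.863, so 0.857 is plausible. No stated power is in question.

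**3. False-claim rate.** A two-sided 95% lower-bound rule is nominally a one-sided 0.025 test. (The simulated PFS error under the null is 0.027 to 0.031 with the plain interval under these two censoring patterns, so the figures here are nominal.) With both nulls true and each endpoint claimed separately, the chance of at least one false claim is 1 − P(Z1 < 1.96, Z2 < 1.96):

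| Assumed correlation | Separate claims | Fixed order |
|---|---|---|
| 0 | 1 − 0.975² = 0.0494 | 0.025 |
| 0.3 | 0.0476 | 0.025 |
| 0.5 | 0.0454 | 0.025 |
| 0.7 | 0.0417 | 0.025 |

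PFS counts deaths in the same subjects, so positive correlation is expected and 0.0494 is the upper end of this table. If ORR is counted as a third ungated test, independence gives 1 − 0.975³ = 0.0731, with an upper bound of 3 × 0.025 = 0.075.

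**4. How often the readings would part.** At the stated powers, P(PFS fails and OS passes) under independence is (1 − 0.877) × 0.857 = 0.105. With bivariate normal correlation it is 0.089 at 0.3, 0.075 at 0.5, 0.056 at 0.7 and 0.029 at 0.9.

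**5. A reachable example.** Take n = 57 with no censoring before the landmark, and the plain bound p − 1.96·√(p(1−p)/n).
- PFS 35/57 = 0.614: 0.614 − 1.96 × 0.0645 = 0.488, below 0.50, so it fails.
- OS 33/57 = 0.579: 0.579 − 1.96 × 0.0654 = 0.451, above 0.44, so it passes.

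Log-log bounds (0.475 and 0.441) give the same result for both.

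**6. Analysis set.** Protocol 9.7.1.2 and 9.7.1.6.4 and SAP 5.2.1 make the EAS primary for efficacy, with FAS efficacy analyses in addition. SAP 5.4.2 assigns all secondary efficacy analyses to the FAS. That departs from the protocol, and section 7 does not list it.

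**The case against.** The strongest reply is that nothing has been dropped. SAP section 3 says the SAP covers the analyses in the final protocol, so rules it does not repeat may still be in force. SAP 5.1.2 and 5.4.2 also name PFS before OS, the protocol's order. The protocol's OS rule is unconditional as worded, no stop rule exists in either document, and a list that includes medians without null values cannot be gated throughout. On that view, sequential analysis means only the order of working, and each endpoint stands on its own interval.

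Much of this stands. A reader might infer that the SAP abandoned a fixed testing sequence the protocol had promised, or that 2.5% was a documented commitment. Neither is supported: a fixed order is one natural reading of the protocol sentence, but the protocol never writes the condition that makes it a gate. The SAP's silence on order is therefore not shown to be a deviation. A reader might also infer that the move to the FAS changes which claims succeed. The documents do not give the size of the FAS, so that effect cannot be computed.

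The reply does not explain why the SAP refers to tests and powers them but gives no criterion, and it does not cover the change from EAS to FAS. It is also fair that the effect is modest: at most 2.5 percentage points of nominal error, confined to secondary endpoints of a single-arm Phase 2 trial.

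**Conclusion.** The point holds as a gap in the decision rules plus one unrecorded deviation. The deviation is the move of all secondary efficacy analyses from EAS to FAS. The gap is that neither document settles whether 6-month OS may be claimed when 12-week PFS fails, or whether either needs ORR to succeed, and the SAP states no threshold as an analysis rule.

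Separate claims carry a nominal one-sided false-claim rate of about 4.2% to 4.9% (assumed correlation 0.7 to 0) across the two secondary endpoints, against 2.5% under a fixed order. The 3% to 11% chance that PFS fails and OS passes rests on the stated powers for 57 evaluable subjects and an assumed correlation of 0.9 to 0. Because SAP 5.4.2 uses the FAS, that range is illustrative. The primary ORR test is not affected.

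**What to change.** Before database lock, choose one of two options.

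**Option 1: ordered claims.** State in SAP 5.3.3 and 5.4.2, and clarify in protocol 9.7.1.6.2: *In the EAS, and only if the primary ORR test succeeds, 12-week PFS (lower two-sided 95% bound above 50%) and then 6-month OS (lower bound above 44%) are tested in that order, each at one-sided 0.025. If a step fails, later endpoints are descriptive. Median PFS and median OS are descriptive. FAS results are supportive.*

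**Option 2: no claims.** Declare all secondary endpoints descriptive, make no significance statements on them, and record this and the choice of FAS in SAP section 7.

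Option 1 costs a few SAP sentences and a short protocol clarification. Its price is no OS claim when PFS fails (about 3% to 11% of trials at the stated powers, assumed correlation 0.9 to 0), and no PFS or OS claim when ORR fails (1 − 0.932 = 6.8% at the stated ORR power). Option 2 costs a section 7 entry and matching wording in 5.3.3, but gives up significance statements on two endpoints for which power was calculated.

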### 5.3.4 Examination of Subgroups

No examination of subgroups is planned.

### 5.3.5 Handling of Missing Data, Dropouts, and Outliers

Rules of handling missing or partial missing dates are explained in [Section 8](#). The censoring rules used in time-to-event analyses (PFS, OS, DOR) are also explained in [Section 8](#). Potential outlier values will be investigated, and they will be analyzed as originally reported in the locked database.

In the analyses on the endpoints described above and any sensitivity analysis, subjects with missing data will be considered as non-responders and will be included in the denominator when calculating ORR, DCR, and CBR. Non-responders will be excluded in the analysis of DOR.

### 5.3.6 Other Considerations

Not applicable.

## 5.4 Efficacy Analyses

### 5.4.1 Primary Efficacy Analyses

In the study design, the ORR was estimated as 27% (deemed a clinical meaningful improvement), and its historical control on recent trials was assumed to be 10%. The study primary analysis was planned to be performed for the observed ORR using the binomial exact test, on evaluable analysis set, and based on the following hypotheses

$$H_0: \text{ORR} = 10\%$$

$$H_a: \text{ORR} \geq 27\%.$$

And in the plan if the obtained p-value from the binomial exact test was less than or equal to 0.025 (one-sided), it would be concluded that the superiority of single agent lenvatinib was demonstrated.

The 95% Clopper–Pearson confidence interval (95% CI) of ORR will be presented. The same primary efficacy analysis for ORR for evaluable analysis set will also be repeated for the full analysis set.

### 5.4.2 Secondary Efficacy Analyses

All analyses of secondary efficacy endpoints will be performed in FAS.

Progression-Free Survival (PFS) and Overall Survival (OS) will be analyzed using Kaplan-Meier product-limit method. The Kaplan-Meier estimated rate of event-free will be presented at 12 weeks for PFS and at 6 months for OS, together with the corresponding two-sided 95% CI. In addition, the median, first and third quartiles of the Kaplan-Meier estimated event-free time will also be presented together with the corresponding 95% Brookmeyer-Crowley (or generalized Brookmeyer-Crowley) CI.

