9.7.1.2 Definitions of Analysis Sets

Full Analysis Set (FAS) will include all subjects who received at least one dose of lenvatinib. The FAS will be the population for the safety analysis. Some selected efficacy endpoints will also be summarized in the FAS.

Evaluable Analysis Set (EAS) will include FAS subjects with histological diagnosis of ATC that is confirmed by central pathology review. The EAS will be the primary population for the efficacy analysis.

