9.7.1.8.6 OTHER SAFETY ANALYSES

9.7.1.9 Other Analyses

Primary, secondary and exploratory endpoints will be summarized in the evaluable analysis set in which central confirmed ATC is required. In the analyses described above and any other sensitivity analysis, subjects with missing data will be considered as non-responders and will be included in the denominator when calculating ORR, DCR, and CBR. Non-responders will be excluded in the analysis of DOR.

Any other statistical/ analytical issues will be discussed in the SAP.

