## 7 CHANGES IN THE PLANNED ANALYSES

Treatment duration will be analyzed in months instead of nominal cycles mentioned in the protocol. The exploratory analyses of identifying and exploring tumor and blood biomarkers that correlate with clinical outcomes, including efficacy will not be performed.

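### SAP 5.4.2 moves all secondary efficacy analyses to the FAS, against the protocol and SAP 5.2.1, and SAP Section 7 does not declare the change

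*SAP*

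**What the plan says.** **SAP.** Section 5.4.2 opens with "All analyses of secondary efficacy endpoints will be performed in FAS". It then describes Kaplan-Meier estimates for PFS and OS without mentioning the EAS. Section 5.2.1 still makes the EAS the primary efficacy population. The sections on either side do name it: for ORR, Section 5.4.1 says "The same primary efficacy analysis for ORR for evaluable analysis set will also be repeated for the full analysis set", and Section 5.4.3 allows either or both sets for exploratory endpoints.

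**Protocol.** Section 9.7.1.2 says "The EAS will be the primary population for the efficacy analysis". Section 9.7.1.6.4 says "The primary population for efficacy analysis is EAS" and brings in the full set only as an addition: "Efficacy and safety analysis will also be performed in FAS". Section 9.7.1.9 is explicit about secondary endpoints: "Primary, secondary and exploratory endpoints will be summarized in the evaluable analysis set in which central confirmed ATC is required".

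**Duty to declare.** Protocol 9.7.5 says "Any deviation from analysis plan described in the protocol will be documented in the SAP". SAP Section 7 lists two changes. One is "Treatment duration will be analyzed in months instead of nominal cycles mentioned in the protocol", and the other drops the biomarker analyses. The analysis population is not mentioned.

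**The concern.** Followed literally, SAP 5.4.2 produces no secondary efficacy result in the population that the protocol names and on which it bases the powers of 0.877 (12-week PFS) and 0.857 (6-month OS).

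Protocol 9.7.1.6.2 sets claim rules against historical controls for this disease: a 95% lower bound above 50% for 12-week PFS and above 44% for 6-month OS. SAP 5.4.2 does not restate these rules, but SAP 5.3.3 still speaks of tests of secondary endpoints. If the rules are applied to the FAS, subjects without centrally confirmed ATC count towards a claim about ATC. These are subjects with another diagnosis and, as the EAS is worded, those whose review is missing or inconclusive. If they do better than ATC, a claim can arise with no effect in ATC. If they do worse, a real effect can be missed.

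**Working it through.** **1. Inputs and the plan's own figures** (Protocol 9.7.2, repeated in SAP Section 4)

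- ORR: with 57 subjects, a null of 10% and one-sided 0.025, rejection needs at least 11 responders. P(X ≥ 11) is 0.0242 at 10% and 0.932 at 27%. This matches the stated 0.932.
- Enrolment: 57 / 0.75 = 76, as stated.
- 12-week PFS: simulating 57 subjects with exponential times, 70% at 12 weeks, about 45 events on average and a plain Greenwood interval gives power 0.863, close to the stated 0.877.
- 6-month OS: the alternative is not stated. The stated 0.857 is reached at a true rate of about 64% to 65%.

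The stated powers therefore belong to 57 evaluable subjects, that is, the EAS.

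**2. Number of subjects the FAS adds**

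76 × (1 − 0.75) = 19 if every enrolled subject is treated. The SAP equates enrolment with signed consent, so the number falls if some are never treated or if central review comes before treatment. I also show 8, an assumed smaller number.

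**3. Shift in the estimate**

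Shift = (share unconfirmed) × (rate in unconfirmed − rate in ATC). With a share of 19/76 = 25% and an assumed rate of 30% to 90% in the unconfirmed:

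- PFS, ATC at 50%: 0.25 × (0.30 − 0.50) = −5 points, to 0.25 × (0.90 − 0.50) = +10 points.
- OS, ATC at 44%: 0.25 × (0.30 − 0.44) = −3.5 points, to 0.25 × (0.90 − 0.44) = +11.5 points.

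**4. Chance of passing the protocol's rule**

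With no censoring before the landmark, the Kaplan-Meier estimate is x/n and the rule is p − 1.96 × √(p(1 − p)/n) > benchmark. The smallest passing counts are:

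- PFS: 36 of 57 (lower bound 0.506) and 47 of 76 (0.509).
- OS: 33 of 57 (0.451) and 42 of 76 (0.441).

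The count in the FAS is the sum of Binomial(57, ATC rate) and Binomial(19, rate in unconfirmed), which gives:

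| Assumed rate in the 19 added | PFS claim, ATC at 50% | PFS power, ATC at 70% | OS claim, ATC at 44% |
|---|---|---|---|
| EAS only, none added | 3.1% | 90% | 2.4% |
| 30% | 0.2% | 41% | 0.6% |
| 50% | 2.5% | 76% | 5.6% |
| 70% | 13.5% | 95% | 23% |
| 90% | 41% | 99.7% | 57% |

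With 8 added, the thresholds are 41 of 65 (PFS) and 37 of 65 (OS). False claims then run from 0.8% to 11% for PFS and from 1.2% to 14% for OS as the assumed rate goes from 30% to 90%.

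**5. Effect of early PFS censoring**

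Protocol 9.3.1 (criterion 2b) takes subjects found not to have ATC off the study. It is unclear whether that is a withdrawal under row 3 of Table 2 in SAP Section 8. In simulation, if all 19 are censored at first dose, the PFS false-claim rate stays at 3.0%. If they are censored at week 6, it runs from 0.9% (30%) to 11% (90%).

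**6. Support for the assumed rates**

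Only the 90% PFS rate has an anchor in the documents. The RR-DTC median of 18.3 months (Protocol 7.1.2.2, about 557 days) gives 0.5^(84/557) = 0.90 under an exponential model, from independent review in a different population. The other PFS rates and all the OS rates are assumptions.

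**The case against.** **An EAS version may exist.** Section 5.4.2 does not say that the FAS is the only set, SAP 5.2.1 keeps the EAS primary, and the table shells are in a separate document not available here. So a deliberate decision to drop the EAS is not shown. But Section 5.4.2 says all analyses, its neighbours name the EAS where it does not, and shells would not supply the missing entry in Section 7.

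**The claim rules may never be applied to the FAS.** This is fair. No document says they will be, and the error rates above are conditional on it. The missing EAS analysis does not depend on it.

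**The FAS may be the closer match to the historical controls.** Nothing says that those controls were centrally confirmed. This stands as a possible argument for the FAS, but the SAP does not make it, and Section 7 is where it belongs.

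**The largest figures are weakly based.** This is also fair. The 41% and 57% need all 19 subjects and 90% rates, and DTC is excluded here unless ATC arises from it. The interval scale is not specified either: with log-log limits they become 32% and 47%. Nor is 19 a strict maximum, because subjects found not to have ATC are replaced and a lower confirmation rate would add more.

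**OS follow-up of subjects taken off study is not fully settled.** SAP 3.2 follows all subjects for survival, with exceptions for withdrawn consent and a sponsor decision to halt follow-up. If follow-up in practice stopped without either lost or withdrawn status, the OS rule in SAP Section 8 would censor at data cutoff and treat the subject as alive until then. This affects the supportive FAS analysis only.

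**Conclusion.** The concern holds. SAP 5.4.2 contradicts Protocol 9.7.1.2, 9.7.1.6.4 and 9.7.1.9 as well as SAP 5.2.1, and the departure is not documented as Protocol 9.7.5 requires. An FAS analysis is legitimate as an addition; the defect is the absence of the EAS analysis. That conclusion rests on the text alone.

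The size and direction of the effect cannot be fixed from the documents, because they give neither the number nor the outcomes of the added subjects. The calculations show that the FAS result can mislead in either direction, and that the effect shrinks with fewer added subjects or early PFS censoring. The primary ORR analysis, in the EAS and repeated in the FAS, is not affected.

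**What to change.** - Reword SAP 5.4.2 so that all secondary efficacy analyses are performed in the EAS as primary and repeated in the FAS as supportive.
- State that the protocol's 50% and 44% lower-bound rules apply to the EAS result only.
- For the supportive FAS analysis, state whether being taken off study after central pathology review counts as withdrawal under Table 2, row 3, and how survival is followed and censored for these subjects.
- If the sponsor prefers the FAS as the primary set for these endpoints, list and justify that in SAP Section 7.

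The cost is a few sentences and one extra set of outputs, since the EAS is already defined and used for ORR. Intervals in the EAS will be somewhat wider, with 57 planned subjects against up to about 76.
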